3.0 Study Design

This study will employ a "pre-post" pragmatic design, which will consist of both a pre-period, or an observational baseline period, and a post-period, or an interventional period. The pre-period and post-period will consist of independent groups of patients. During the pre-period, each participating site will implement the first component of the critical pathway through implementation of guideline-based criteria to identify patients at the point of care in the ED, obtain informed consent, and monitor enrolled patients. Sites will initiate treatment for ABSSSI with "usual care," defined as site- or physician-specific antibiotic treatment of ABSSSI with coverage for a known or suspected Gram-positive infection (e.g., vancomycin, linezolid, and daptomycin) to each study patient who meets all inclusion and exclusion criteria. Blinding of treating physician to patient enrollment in the study during the pre-period will ensure unbiased provision of usual care. During the post-period, for all patients who provide informed consent and are subsequently enrolled, each participating site will additionally implement the second component of the new critical pathway, use of dalbavancin, at the point of care in the ED to each study patient who meets all inclusion and exclusion criteria. Sites are expected to transition to the post-period at the enrollment of 50 patients. There is no expectation for all sites to transition to the post-period at the same time.

For both periods of interest, patient follow-up spans the period beginning on the day of study enrollment and ends 44 days thereafter, which incorporates an initial care period of 14 days (reflecting the 10–14-day period during which most antibiotics are anticipated to be required for care of ABSSSI) and a subsequent “follow-up” period of 30 days. Study measures will be collected as described in the protocol and will be based on medical records, unless otherwise indicated.

A schedule of assessments is provided in Appendix A. Follow-up visits will be scheduled for approximately 24 hours after enrollment (post-period only), 48–72 hours after enrollment (post-period only), 14 days after enrollment (both periods), and 44 days after enrollment (both periods). Any additional visits to the visit schedule below will be at the discretion of the patient and treating physician.

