5.0 Changes in the Protocol Specified Analyses

Infection characteristics described in the protocol including hyperglycemia (>120mg/dL blood glucose or site-specific definition), thrombocytopenia (<150,000 platelet count or site-specific definition), acidosis (<7.35 pH of the blood or site-specific definition or described in medical chart), hyponatremia (<135 mEq/L blood sodium or site-specific definition), uremia (as described in medical chart), and anemia (14-18 g/dL hemoglobin for men or 12-16 g/dL hemoglobin for women or site-specific definition) will not be derived from laboratory values or reported in analysis.

An interim analysis was performed after the enrollment of approximately 75 patients to evaluate the original sample size. It was determined a sample size greater than 322 would be needed for hypothesis testing of the primary outcome of total number of days spent in the hospital. Factors that contributed to the large sample size include:

- The observed variation was larger than the original estimate (SD = 3.0 days).
- The observed attrition rate was larger than the original assumption (10%).

Additionally, the observed mean total LOS was much smaller than the protocol assumption (4.0 days). It was determined that observing a statistically significant reduction in the total number of days spent in the hospital in the post-period was unlikely.

Based on results of the interim analysis, an adjustment was made at the time of the analysis to revise the primary outcome from total admitted hospital days to hospital admission rate at initial episode of care. The initially estimated final enrollment of 322 subjects, including adjustments for attrition, would support one-sided hypothesis testing (two-sample Pearson chi-square test for proportion difference with equal group weights using a normal approximation) with a significance level of 0.05 and at least 80% power assuming hospital admission rate comparing the pre- and post-periods were 38% versus 23%. This change has been reflected in the protocol, Amendment Version 3.0.

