6.1.2 Sample size

Hospital admission rate, which is correlated to total hospital time for the study population, was largely unknown for purposes of sample size estimation. The final enrollment to support hypothesis testing for a primary outcome of total admitted hospital days was initially calculated as 322 subjects (161 subjects in each period). The sample size was evaluated after a planned interim analysis of pre-period data once 75 subjects were enrolled in the pre-period. Based on results of the interim analysis, an adjustment was made at the time of the analysis to revise the primary outcome from total admitted hospital days to hospital admission rate at initial episode of care. The initially estimated final enrollment of 322 subjects, including adjustments for attrition, would support one-sided hypothesis testing (two-sample Pearson chi-square test for proportion difference with equal group weights using a normal approximation) with a significance level of 0.05 and at least 80% power assuming hospital admission rate comparing the pre- and post-periods were 38% versus 23%.

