6.1.3 Rounding

Means and medians will be rounded to one decimal more than that which the variable was recorded. Standard deviations will be rounded to two decimals more than that which the variable was recorded.

Percentages will be rounded to the nearest integer. Percentages for responses to a variable will only include patients with non-missing data, i.e. the denominator will be the number of patients with non-missing data.

P-values will be reported to three decimal places. Probabilities that are <0.001 will be presented as " <0.001 ."

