6.1.5 Handling of missing and/or incomplete data

Patients will be missing specific data points for a variety of reasons. With the exception of validated instruments, missing values for a given time point will not be imputed and analyses will be conducted using an observed case approach. For validated instruments, missing items will be handled according to instructions from the relevant scoring manuals.

Where both date and time are collected, partial times (i.e. times with missing minutes or times with missing hours and minutes) will be estimated by a worst-case imputation approach (e.g., impute such that duration is the longest possible value). Analyses will be conducted using an observed case approach for partial or missing dates.

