Infection-related hospitalizations will be displayed in tables by initial care, follow-up, and overall by the pre-period and post-period for the FAS

population. Patient counts and percentages will be reported for none, any, 1, 2, and ≥ 3 infection-related hospitalizations. No formal hypothesis testing will take place.

Secondary Outcomes: Infection-Related Hospitalizations that Resulted in Admission to Intensive Care Unit (ICU)

Infection-related hospitalizations that resulted in admission to ICU will be displayed in tables by initial care, follow-up, and overall by the pre-period and post-period for the FAS population. Patient counts and percentages will be reported for none, any, 1, 2, and ≥ 3 infection-related hospitalizations that resulted in admission to ICU. No formal hypothesis testing will take place.

Secondary Outcomes: All Cause Hospitalizations in the 30 Days Post-Discharge from the Hospital or Release from ED

All-cause hospitalizations in the 30 days post-discharge from the hospital will be displayed in tables by the pre-period and post-period for the FAS population. Patient counts and percentages will be reported for none, any, 1, 2, and ≥ 3 all-cause hospitalizations in the 30 days post-discharge from the ED. No formal hypothesis testing will take place.

Secondary Outcomes: Infection-Related ED Visits

Infection-related ED visits will be displayed in tables by initial care, follow-up, and overall by the pre-period and post-period for the FAS population. Patient counts and percentages will be reported for none, any, 1, 2, and ≥ 3 infection-related ED visits. These categories will be repeated for all, expected, and unexpected ED visits. No formal hypothesis testing will take place.

Secondary Outcomes: Infection-Related Outpatient Healthcare Visits

Infection-related outpatient healthcare visits will be displayed in tables by initial care, follow-up, and overall by the pre-period and post-period for the FAS population. Patient counts and percentages will be reported for none, any, 1, 2, and ≥ 3 infection-related outpatient healthcare visits. These categories will be repeated for all, expected, and unexpected outpatient healthcare visits. No formal hypothesis testing will take place.

Secondary Outcomes: Use of PICC Line or Central Line to Administer Antibiotic Therapy

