Secondary Outcomes (All visits)	Hospitalization LOS (days)	
For all-cause: Σ (Hospitalization end date – Hospitalization start date +1), when both dates are available. If ongoing at end of study or discontinuation date, use study completion date or discontinuation date as end date. For outcomes, LOS will be computed two ways: only in-patient hospitalizations visits and inpatient hospitalizations visits with prolonged observation

[figure not shown]
Analysis Section (Visit)	Variable (Units)	Definition
		
status (e.g., time in observation status exceeds 1 day).
 
For infection-related: Subset all-cause hospitalization time for patients with infection-related hospitalization stays

Secondary Outcomes (End of Study Visit)	Completers Flag	
If "Did the patient complete the study?" = 1 on the end of study visit CRF page and date of study completion does not equal missing, then =Yes, Else = No
 
This flag will be used to repeat certain primary and secondary outcomes that could be influenced by early discontinuation (e.g., LOS)

Secondary and Other Outcomes (Initial episode of care)	ED LOS (hours) Observation Status LOS (hours)	
Impute with estimated time where applicable for partial times. if admission date = discharge date then LOS (hours) = discharge time - admission time
 
else LOS (hours) = sum all hours over stay, with a full day counting as 24 hours

Secondary Outcomes (Follow-up)	WPAI	Scores and coded variables will be derived as described in Appendix D.
Secondary Outcomes (Initial Care and Follow-up)	SF-12	SF-12 sub-scores and total scores will be compiled using the Health Outcomes Scoring Software 5.0 by QualityMetric Inc. Further detail can be found in Appendix E.
Adverse Events (Baseline, Initial Care and Follow-up)	Highest severity AE	Severity of most severe AE for the patient with order of severity: Severe>Moderate>Mild Patients who only have AEs reported with missing severity,

Analysis Section (Visit)	Variable (Units)	Definition
		highest severity AE will be reported as missing

[Redacted]

[Redacted]

[Redacted]

[Redacted]

[Redacted]

[Redacted]

[Redacted]

[Redacted]

[Redacted]

[Redacted]

[Redacted]

[Redacted]

[Redacted]

[Redacted]

[Redacted]

[Redacted]

[Redacted]

[Redacted]

[Redacted]

[Redacted]

[Redacted]

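### The 44-day hospitalisation, visit and SAE tables make no allowance for unequal observation time, and the SAP does not say how a patient lost before day 44 is counted

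*SAP*

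**What the plan says.** SAP 3.0 sets the observation window: "patient follow-up spans the period beginning on the day of study enrollment and ends 44 days thereafter". SAP 4.4 and 6.2.5.2 define the cumulative outcomes over that window. For hospitalisations, "Patient counts and percentages will be reported for none, any, 1, 2, and ≥ 3 infection-related hospitalizations"; ED, outpatient and line-related visits follow the same layout, for initial care, follow-up and overall. SAEs are given as events, patients and percentage of patients. None of these has a person-time denominator, a censored estimate or a minimum follow-up requirement. The full analysis set (SAP 6.1.1) requires enrolment and one dose, nothing more.

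On missing data, SAP 6.1.5 says that, validated instruments apart, there is no imputation and "analyses will be conducted using an observed case approach". SAP 6.1.3 adds that for percentages "the denominator will be the number of patients with non-missing data". Neither section says how a patient lost before day 44 enters a 44-day count. Protocol 5.2 had left the handling of subjects lost to follow-up for the SAP to define.

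SAP 5.0 reports that attrition at the interim look exceeded the 10% first assumed. SAP 6.1.2 identifies that look as a "planned interim analysis of pre-period data once 75 subjects were enrolled in the pre-period". Appendix B provides a completers flag for certain outcomes sensitive to early discontinuation, with length of stay as its example. Section 6.2.5.2 specifies a completer repeat only for total hospital days.

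**The concern.** A 44-day count depends on how long the patient was watched. If one period loses more observation time, a comparison of raw counts or percentages mixes the event rate with the length of observation. Unequal loss is plausible: only the post-period has scheduled contacts at 24 hours and 48–72 hours (Protocol 3.2.1; SAP 3.0), and the discontinuation reasons in Protocol 2.5 include adverse events, so leaving may be related to outcome.

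These tables carry the trial's comparison of safety and of healthcare use after the index visit, and the 44-day costs in SAP 6.2.12 are built from the same utilisation data. A reader who sees fewer SAEs or visits in one period could not tell from them whether there were fewer events or fewer days observed.

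**Working it through.** **Plan's own figure.** The documents state at least 80% power with 322 patients, 38% v 23%, one-sided 0.05. With n = [1.645·√(2·0.305·0.695) + 0.842·√(0.38·0.62 + 0.23·0.77)]² / 0.15², n = 116 per period. With 161 per period, power is 90.2%; it is 87.4% at 10% attrition and 83.7% at 20%. The statement reproduces and stays true up to about 28% attrition (1 − 116/161). So the higher attrition matters here for the 44-day outcomes, not for the power of the primary test.

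**Inputs.** Window 44 days = 14 initial care + 30 follow-up (SAP 3.0, Appendix B). Attrition: only that it exceeded 10% in about 75 pre-period patients. The rates by period, the time of leaving and the event risks below are assumptions.

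**Event counts.** Let a proportion d leave at day 14, with a constant event rate and no later capture. The observed share of person-time is 1 − d·30/44.

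| Attrition | Share observed | Mean days |
|---|---|---|
| 5% | 1 − 0.05·30/44 = 0.966 | 42.5 |
| 15% | 1 − 0.15·30/44 = 0.898 | 39.5 |
| 20% | 1 − 0.20·30/44 = 0.864 | 38.0 |

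- 20% v 5%: 0.966/0.864 = 1.12, so equal true rates appear 12% higher in the period with less dropout.
- 15% v 5%: 0.966/0.898 = 1.08.
- In the separate follow-up column, where day-14 leavers contribute nothing: 0.95/0.80 = 1.19 and 0.95/0.85 = 1.12. The initial-care column is unaffected.
- Equal attrition: ratio 1.

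**Percentage with any event, leavers counted as 'none'.** With true 44-day risk P, a leaver has risk q = 1 − (1 − P)^(14/44) before leaving, and the observed percentage is (1 − d)·P + d·q.

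| True risk P | 10% attrition | 20% attrition | Spurious gap, points (day-14 exit) | Gap, other exit patterns |
|---|---|---|---|---|
| 10% | 9.33% | 8.66% | 0.67 | 0.5–1.0 |
| 20% | 18.69% | 17.37% | 1.31 | 1.0–2.0 |
| 40% | 37.5% | 35.0% | 2.5 | 1.8–4.0 |

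The last column runs from exits spread evenly over 44 days to all exits at enrolment.

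**Same case, event-free leavers excluded as missing.** With P = 20%, q = 0.0685. At 20% attrition the percentage is 0.1737/(1 − 0.20·0.9315) = 21.3%; at 10% it is 0.1869/(1 − 0.10·0.9315) = 20.6%. The gap is 0.7 points in the opposite direction, because leavers with an event stay in and those without drop out. The unstated rule therefore settles the sign as well as the size.

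**The case against.** A reader might infer that the SAP treats every patient as observed for all 44 days, so that the period with more dropout is bound to look better. The documents do not say that. SAP 6.1.5 and the non-missing denominator in 6.1.3 could equally be read as excluding an unobserved patient. The plan is silent on the rule.

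A reader might also take the attrition statement as evidence of unequal dropout. It comes from about 75 pre-period patients; no post-period rate exists. If the early post-period contacts did improve retention, counting leavers as 'none' would work against the new pathway rather than for it.

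Other points stand in part:

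- Protocol 3.2.1 has charts reviewed at days 14 and 44 in both periods, so some events after lost telephone contact would be found. Protocol 7.3 ends data collection when consent is withdrawn, and care outside the site's records may be missed.
- Many events will be early. Infection-related hospitalisations include index admissions, which precede any dropout and dilute the distortion.
- The completers flag is not limited to length of stay, which is only its example. But the other outcomes it covers are not named, and completers are a selected group.
- These outcomes receive no formal test, and disposition and discontinuation dates are reported. That limits the consequence but does not put counts on a common observation time.

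**Conclusion.** The gap is real and minor. Cumulative 44-day outcomes are compared without regard to observation time, and the SAP does not supply the counting rule that the protocol left to it. A between-period bias is possible but not shown; its direction depends on which period loses more follow-up and on how early leavers are counted.

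The 12% and 8% figures are illustrations. They rest on assumed attrition, exit at day 14, a constant event rate and no later capture by chart review. With equal attrition and the same pattern of leaving they vanish, and chart review and early events would shrink them. For the percentage with any event, 10% v 20% attrition gives gaps of about 0.5 to 4 points over assumed risks of 10% to 40% when leavers count as 'none'.

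The effect is confined to the descriptive secondary, safety and cost summaries. The primary outcome is fixed at the index episode and is not touched by later loss to follow-up.

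**What to change.** 1. In SAP 6.1.5, define each patient's end of observation as the later of last contact and last completed chart review, capped at day 44 (enrolment date + 43 in Appendix B) and ending at withdrawal of consent. State how a patient whose observation ends before day 44 with no recorded event appears in the existing tables.
2. Report observed follow-up time by period.
3. Beside the existing tables, add events per patient-day with a rate ratio and CI, allowing for repeated events within a patient, and the cumulative incidence of any event. Censor at the same end of observation; censoring at discontinuation would discard events found later by chart review that the rates include.
4. Note that both estimates assume dropout is unrelated to event risk. They put the periods on a common observation time but do not correct for informative dropout.

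The cost is a few extra table columns. Discontinuation and completion dates are already listed (SAP 6.2.1); the date of the last completed chart review must also be available.

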3.2.1 Data collection schedule

Table 5 describes expected follow-up. Follow-up visits will be scheduled for 24 hours after enrollment (post-period only), between 48-72 hours after enrollment (post-period only), 14 days after enrollment (both periods), and 44 days after enrollment (both periods). The follow-up visits during the post-period include a telephone call at 24 hours and a limited physical visit at 48-72 hours. However, for subjects unable to be seen back at the site, a telephone interview will suffice at 48-72 hours. Research data will be collected through follow-up visits at 14 days (telephone call can occur between 14 and 21 days from enrollment) and at 44 days (telephone call can occur between 44 and 51 days from enrollment), through a telephone interview of the subject in both the pre- and post-periods. Additionally, electronic medical chart data will be reviewed at the 14 day and 44 day time points from enrollment. Any additional visits to the visit schedule below will be at the discretion of the subject and treating physician.

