3.2.2 Patient Diary Aid

Patients will be provided with a bound, paper diary to record specific information about their health status on days in which they have an interaction with a health care provider. The diary is intended only as an aid to help patients remember details about health care appointments, medications, and medical tests. The diary will not be collected by or returned to study staff.

4 Safety assessments

At each visit, subjects are to be queried regarding any adverse events (AEs) or serious adverse events (SAEs) that have occurred since the previous visit. Subjects will be asked to volunteer information with a nonleading question such as, “How do you feel since your last visit?” Study site personnel will record all pertinent information in the subject’s CRF. All AEs will be recorded on the appropriate AE reporting page of the subject’s CRF whether or not they are considered causally related to the study drug (any antibiotic given for ABSSSI from enrollment, including the pre-period).

For every AE, the investigator will:

- Provide an assessment of the seriousness of the event (i.e., is it an SAE?), as well as the severity and causal relationship
- Document all actions taken with regard to the study drug
- Detail any other treatment measures taken for the AE
- Document the outcome of the AE

In addition, subjects will be reminded, as described in the ICF to notify site personnel of any AEs occurring from the time the subject signed the ICF until the final follow-up visit. Any AEs that are ongoing at the time of the final protocol-defined study visit will be followed until the condition returns to pre-study status, has resolved or stabilized, or can be explained as being unrelated to the study drug. If a follow-up visit is deemed necessary for appropriate safety surveillance, it will take place within 30 days of the final protocol-defined study visit.

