Appendix B: Derived Variables

Analysis Section (Visit)	Variable (Units)	Definition
General (Baseline)	Enrollment date	Informed consent date
General (Baseline)	Baseline date	Initial ED admission date
General (Initial Care)	Initial care indicator	If enrollment date \leq date \leq enrollment date + 13 days then = Yes Else = No
General (Follow-up)	Follow-up indicator	If enrollment date + 14 \leq date \leq enrollment date + 43 days then = Yes Else = No
Demographics (Baseline)	Age (years)	Round down to nearest integer((Initial ED admission date - date of birth + 1)/365.25), when both dates are available.
Demographics (Baseline)	BMI	weight (kg)/ [height(m)] ² Where necessary, height and weight will be converted to proper units.
Infection Characteristics (Baseline)	CCI	Will be scored as described in Appendix C. Includes variables for raw score and 10 year survival probability.
Infection Characteristics (Baseline)	Fever	If temperature > 38 ° C then =Yes Else =No
Infection Characteristics (Baseline)	Morbid Obesity	If baseline BMI \geq 40 then =Yes Else =No
Infection Characteristics (Baseline)	SIRS Criteria Met	SIRS criteria include abnormalities in temperature, heart rate, respiration, and white blood cell count. Specifically included are: 
 Fever of more than > 38.0°C or hypothermia with temperature < 36.0°C

[figure not shown]
[figure not shown]
Analysis Section (Visit)	Variable (Units)	Definition
		
 • Tachycardia with heart rate > 90 beats/minute or • Tachypnea with respiratory rate of > 20 breaths/minute or PaCO₂ of less than 32mmHg • Abnormal white blood cell count: leukocytosis >12,000/microliter, leucopenia <4,000/microliter, or >10% immature cells (bands).^{3,4} 
If 2 or more criteria present = Yes Else = No

Antibiotic Medications (Initial Care and Follow-up)	Days Received Antibiotic Medication	
Σ (Medication end date – Medication start date +1), when both dates are available. If dates overlap (e.g., end date and next start date are identical) then subtract 1 from summation for each occurrence.

Primary Outcome	Hospital Admission At Initial Episode of Care	
If discharge destination from the initial episode of care = Hospital and the reported hospitalization where discharge date = hospital date is infection-related then = Yes, Else = No

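### A known hospital stay with one incomplete date adds zero hospital days, because the SAP bounds only stays that are still ongoing at study end or discontinuation

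*SAP*

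**What the plan says.** - **Missing values in general (SAP 6.1.5).** Apart from validated instruments, "missing values for a given time point will not be imputed and analyses will be conducted using an observed case approach".
- **Partial or missing dates (SAP 6.1.5).** "Analyses will be conducted using an observed case approach for partial or missing dates".
- **Partial times (SAP 6.1.5).** These "will be estimated by a worst-case imputation approach (e.g., impute such that duration is the longest possible value". Appendix B applies this to ED and observation hours: "Impute with estimated time where applicable for partial times".
- **Hospital days (SAP Appendix B).** Each stay contributes end date minus start date plus 1; the formula ends "Hospitalization start date +1), when both dates are available". A stay still ongoing at study end or discontinuation is closed at that date. Infection-related days are a subset of the same quantity.
- **Time windows (SAP Appendix B).** Initial care runs from enrollment to enrollment + 13 days, and follow-up from + 14 to + 43 days. The follow-up rule ends "enrollment date + 43 days then = Yes Else = No", and the initial-care rule has the same default.
- **Source of the data (Protocol 3.2.1 and 3.2.2).** Research data at the Day 14 and Day 44 contacts are obtained "through a telephone interview of the subject in both the pre- and post-periods", with electronic chart review at both time points. Patients keep a paper diary as a memory aid, but "The diary will not be collected by or returned to study staff".

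**The concern.** An observed-case rule is harmless when a missing date means that nothing is known. Here the stay is known to have occurred and only its length is uncertain. Giving it zero days picks a value that is certainly wrong, since under the SAP's own formula any stay lasts at least 1 day.

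The SAP also does not say whether a patient with such a stay keeps the sum of the remaining stays or is set to missing. The first choice under-counts days. The second removes a patient from the summary because an event occurred. Neither uses what is known.

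The outcomes exposed are total admitted hospital days, infection-related admitted hospital days and the 44-day cost, which multiplies utilization (including hospital days) by unit costs (SAP 6.2.12). Later stays away from the study hospital are plausibly more exposed than index stays, because they may first be learned of by telephone. Date completeness could also differ between periods: the 24-hour and 48–72-hour contacts exist only in the post-period.

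**Working it through.** The plan gives no figure for the frequency of incomplete dates, so there is no stated result to reproduce. The check applies the Appendix B rules to an example and then gauges the scale.

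**Inputs from the documents.** LOS = Σ(end − start + 1) over stays with both dates; windows day 0–13 and day 14–43 (SAP Appendix B). Telephone contacts at days 14–21 and 44–51 (Protocol 3.2.1). 161 patients per period (SAP 6.1.2). Planning values of SD 3.0 days and mean 4.0 days (SAP 5.0, which reports a larger observed SD and a smaller observed mean).

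**1. One patient (assumed dates).** The first stay runs from day 0 to day 3: 3 − 0 + 1 = 4 days. A second stay starts on day 19; its end date is missing and it is not recorded as ongoing.
- SAP rule: 4 + 0 = 4 days.
- Shortest possible: 4 + 1 = 5 days.
- Longest possible within the window: 4 + (43 − 19 + 1) = 4 + 25 = 29 days.
- Midpoint end date, day (19 + 43)/2 = 31: 4 + (31 − 19 + 1) = 17 days.

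The SAP's value lies outside the possible range of 5 to 29.

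**2. Window flags.** If the start date classifies the event, the second stay above (day 19) falls in follow-up despite its missing end date. If the classifying date itself is unusable, neither condition can be confirmed, and the default gives No and No. The SAP does not say which date is used, or whether the flag should instead be missing.

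**3. Overall counts.** SAP 6.2.5.2 tabulates hospitalizations, ED visits and outpatient visits by initial care, follow-up and overall. The both-dates condition belongs to the LOS sum only. No text removes an undated event from the overall counts.

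**4. Scale of the loss in mean days (all shares and lengths assumed).** Loss = share of patients with a later stay × length of stay × share with an incomplete date.
- 0.08 × 4 × 0.25 = 0.08 days.
- 0.10 × 5 × 0.30 = 0.15 days.

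Alternatively, if a share m of all hospital days sits in such stays, a mean of 4.0 would read 4.0 × (1 − m): 3.92, 3.8, 3.6 and 3.2 for m = 2%, 5%, 10% and 20%.

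**5. Comparison with sampling error.** The standard error of the between-period difference, at the planning SD and full enrollment, is 3.0 × √(2/161) ≈ 0.33 days. If the whole loss fell in one period, 0.08 and 0.15 days would be about 0.24 and 0.45 standard errors. Equal losses in both periods would cancel in the difference, though both means would still be too low.

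**The case against.** The case for leaving the rule alone has real content.

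- **Incomplete dates may be rare.** Charts are reviewed at both time points, SAP 3.0 bases measures on medical records unless otherwise indicated, and Protocol 3.2 and 5.4 provide edit checks, queries and site responsibility for supplying missing data. The diary helps patients recall appointment details even though it is not collected. This limits the frequency but does not set it to zero: Protocol 5.2 expects missing data and leaves its handling to the SAP.
- **Some stays are already bounded.** Those ongoing at study end or discontinuation are closed. This stands, and the point excludes them.
- **The stakes are limited.** SAP 6.2.5.2 plans no formal test of hospital days or visit counts. The harm is to estimates, not to error rates.

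Four stronger readings are tempting but not supported.

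- *Return visits and readmissions disappear from the results.* They may leave the by-window rows, but nothing drops them from the overall rows, and a stay with a known start can still be placed in a window.
- *The rule favors the new pathway.* That needs date completeness to differ by period in a known direction. Usual-care stays elsewhere can lose days in the same way.
- *The date and time rules contradict each other.* One acts on hospital days, the other on ED and observation hours. A missing clock time on a known date is confined to that day, so different treatment is defensible.
- *The primary result is distorted.* The primary outcome also requires a date match and otherwise gives No, so a reader might infer that undated index admissions would be counted as not admitted. The documents give no sign that index dates are incomplete: they belong to the visit at which the patient is enrolled. Section 6.1.5 also leaves open whether the result would be No or missing.

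**Conclusion.** The point holds for hospital days. As written, a stay known to have occurred but lacking a usable start or end date contributes nothing to total or infection-related hospital days, unless it is ongoing at study end or discontinuation. The cost summary inherits the loss to the extent that its hospital days are the Appendix B days; SAP section 4.6, cited for cost detail, is not in the public text. For the window tables the weaker statement holds: an event with an unusable classifying date can fall in neither window, while the overall counts are untouched.

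The size cannot be determined. The 0.08 to 0.15 days shown above rests on assumed shares and lengths and illustrates scale only. The direction of any bias in the between-period comparison is also unknown. The outcomes concerned are descriptive, so this is a correction worth making before analysis and not a threat to the primary test.

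**What to change.** Replace the sentence on dates in SAP 6.1.5, and the both-dates condition in the Appendix B LOS entry, with a bounded rule:

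1. Keep in *overall* every event known to fall between enrollment and enrollment + 43 days.
2. Classify the window by start date, using known date parts first. If these do not decide it, use chart information or the contact at which the event was reported only to limit the possible range. Show the event as *window unknown* when the range spans day 13/14.
3. For LOS, impute a missing start or end date at the midpoint of the allowed range, capped at enrollment + 43 days, and repeat with the shortest and longest values.
4. Report the number of imputed dates by period.

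The reporting contact should be a limit and not an assignment. Calls may run to days 21 and 51 while the windows end at days 13 and 43, so assigning events by contact would misplace some and admit others from outside the window. The extra post-period contacts can also make ranges tighter there, which is one reason to report counts by period. The documents do not show that the contact of first report is recorded; where it is not, known date parts, chart information and the window limits supply the range.

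The cost is SAP wording, modest programming and a few imputed dates shown with their bounds. If incomplete dates prove rare, the shortest and longest results will nearly coincide and show it.
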